6.1.2 Treatment Period (2 Weeks)

Subjects will attend study visits at Week 0 (Day 1) + 1 day and Week 2 (Day 15) + 1 day.

Samples for the evaluation of ADA, including titer and NAb (immunogenicity assessments), will be obtained before the administration of study treatment on Day 1 and Day 15.

In the description of evaluations below:

Study Day 1 (Week 0, Baseline Visit)

Eligible subjects will return to the study site for the baseline (Week 0, Day 1) visit. Subjects must satisfy all inclusion/exclusion criteria in order to be eligible for randomization.

Baseline procedures and assessments should be conducted in chronological order as follows:

1. Re-review subject eligibility (inclusion and exclusion) criteria to ensure that the subject continues to be eligible for inclusion into the study. Any questions regarding subject eligibility can be addressed to the medical monitor.
2. Clinical assessments will include the following: physical examination, vital signs measurement (seated BP, heart rate, respiration rate, and oral body temperature).
3. Urine pregnancy test for WOCBP.
4. Clinical laboratory assessments: a blood sample will be taken for hematology and biochemistry; urinalysis will also be performed (see [Section 6.3.4](#) for the list of clinical laboratory assessments).

Note: Viral disease screening (HBsAg, HBcAb, HCV, HIV), and serum IgG and IgM and TB screening will not be repeated on Day 1 of the study. Clinical laboratory assessments scheduled on Day 1 can be performed 1 day prior to dosing.

Note: For HBcAb, site is requested to perform HBcAb IgG and HBcAb IgM. If any of these 2 results is positive, then the subject will be considered as screen failure.

5. Randomize the subject in accordance with the IWRS.

6. Collect plasma samples for immunogenicity assessments prior to administration of study treatment.
7. Collect a time-matched blood sample (approximately 5 mL) for the estimation of rituximab concentration.
8. Study treatment administration and observation for at least an hour post infusion.
9. Assess AE(s).
10. Record concomitant medication(s).

Study Day 15 (Week 2 + 1 Day)

The procedures and assessments are as follows:

1. Clinical assessments will include the following: physical examination, vital signs measurement (seated BP, heart rate, respiration rate, and oral body temperature).
2. Urine pregnancy test for WOCBP.
3. Clinical laboratory assessments: a blood sample will be taken for hematology and biochemistry; urinalysis will also be performed.
4. Collect plasma samples for immunogenicity assessments prior to administration of study treatment.
5. Collect a time-matched blood sample (approximately 5 mL) for the estimation of rituximab concentration.
6. Study treatment administration and observation for at least an hour post infusion.
7. Assess AE(s).
8. Review concomitant medications.

6.1.3 Follow-Up Period (10 Weeks)

Week 4 ± 7 Days

The procedures and assessments for Week 4 ± 7 days are as follows:

1. Clinical assessments will include the following: physical examination (including weight), vital signs measurement (seated BP, heart rate, respiration rate, and oral body temperature).
2. Urine pregnancy test for WOCBP.
3. Clinical laboratory assessments: a blood sample will be taken for hematology and biochemistry; urinalysis will also be performed.
4. Collect plasma samples for immunogenicity assessments.
5. Collect a time-matched blood sample (approximately 5 mL) for the estimation of rituximab concentration.
6. Assess AE(s).
7. Review concomitant medications.

Week 8 ± 7 Days

The procedures and assessments for Week 8 ± 7 days are as follows:

1. Clinical assessments will include the following: physical examination (including weight), vital signs measurement (seated BP, heart rate, respiration rate, and oral body temperature).
2. Urine pregnancy test for WOCBP.
3. Clinical laboratory assessments: a blood sample will be taken for hematology and biochemistry; urinalysis will also be performed.
4. Collect plasma samples for immunogenicity assessments.
5. Collect a time-matched blood sample (approximately 5 mL) for the estimation of rituximab concentration.
6. Assess AE(s).

7. Review concomitant medications.

6.1.4 End of Study/Early Termination Visit (Week 12 ± 7 Days)

Subjects who complete the study or discontinue from the study at any time will attend an EOS/ET visit.

The EOS/ET assessments are as follows:

1. Clinical assessments will include the following: physical examination (including weight), vital signs measurement (seated BP, heart rate, respiration rate, and oral body temperature).
2. Serum pregnancy test (β -hCG) for WOCBP. Female subjects with documented history of hysterectomy, bilateral salpingectomy, bilateral oophorectomy, medically confirmed ovarian failure, or screening FSH test demonstrating postmenopausal status are exempted from pregnancy testing.
3. Clinical laboratory assessments: a blood sample will be taken for hematology and biochemistry; urinalysis will also be performed.
4. Twelve-lead ECG.
5. Collect plasma samples for immunogenicity assessments.
6. Collect a time-matched blood sample (approximately 5 mL) for the estimation of rituximab concentration.
7. Assess AE(s).
8. Review concomitant medication(s).

6.1.5 Additional Follow-Up Visit (Week 26)

The following assessments will be performed at Week 26:

1. Clinical assessments will include the following: physical examination (including weight), vital signs measurement (seated BP, heart rate, respiration rate, and oral body temperature).

2. Serum pregnancy test for WOCBP. Female subjects with documented history of hysterectomy, bilateral salpingectomy, bilateral oophorectomy, medically confirmed ovarian failure, or screening FSH test demonstrating postmenopausal status are exempted from pregnancy testing.
3. Clinical laboratory assessments: a blood sample will be taken for hematology (especially absolute neutrophil count) and biochemistry; urinalysis will also be performed.
4. Twelve-lead ECG.
5. Assess AE(s).
6. Review concomitant medications.

6.2 Immunogenicity Endpoint

The immunogenicity endpoint is the incidence of ADA, including titer and NAb.

6.2.1 Immunogenicity Sampling

Blood samples for detection of ADA (including NAb) will be collected prior to initiation (preferably within 30 minutes) of infusion of study treatment on Day 1 and Day 15 and then on visits at Weeks 4, 8, and 12 (EOS/ET) as specified in [Table 14-1](#) and [Section 6.1](#).

Whole blood samples (approximately 10 mL) will be collected and processed to obtain approximately 4 mL of plasma for ADA (including titer and NAb) detection at each time point. Samples should be processed per detailed instructions in the laboratory manual for collection by the central laboratory. The samples will be shipped to laboratories for ADA titer and NAb analysis by the central laboratory as detailed in the laboratory manual.

Along with the immunogenicity sample, a time-matched blood sample (approximately 5 mL) will be collected for the estimation of rituximab concentration. The evaluation of the samples will be performed to interpret safety and/or immunogenicity data appropriately, if needed.

The central laboratory shipment address and assay laboratories contact information will be provided to the investigator prior to or during the initiation of the study.

Further details on sample collection, processing, and shipment are provided in full in the laboratory manual.

6.2.2 Immunogenicity Assay

Immunogenicity samples will be analyzed by designated analytical laboratory(ies) using validated methods. Analysis of ADA samples will follow a tiered approach of screening, confirmation, and titer determination. Samples that are confirmed positive for ADA will be further tested for titer and NAb using validated assays.

Immunological testing in human subjects will involve a multi-tiered approach as outlined below:

Tier I Screening Assay: All the clinical samples for immunogenicity assessment will be subjected to a screening assay. The methodology is based on the principle of capture of the ADA by the drug and detection by biotin-labelled drug, using ELISA. The test methodology may be modified after the method validation is completed. During method validation, an assay cut point is statistically determined. The samples that show a response equal to or above the pre-determined screening cut point will be called as “screening positive” and the ones that show a response below the assay cut point will be called as “negative”.

Tier II Confirmation Assay: All the clinical samples that are “screening positive” will be subjected to a confirmation assay. This will involve the inhibition of the response seen in the screening assay with high concentration of drug. The assay format is an adaptation of the screening assay, where the samples are spiked with phosphate-buffered saline or drug and incubated for 1 hour at 37°C prior to evaluation according to the screening assay procedure. The samples that show a response equal to or above the pre-determined confirmatory cut point will be called as “confirmed positive” and the ones that show a response below the assay cut point will be called as “negative”.

[figure not shown]
Tier III Titer Determination: It is the semi-quantitative assay where titers of the confirmed ADA-positive samples will be evaluated with respect to a previously established titer cut point. During the clinical sample analysis, serial 2-fold dilutions of confirmed positive samples will be performed and the reciprocal of the dilution able to yield a response at or above the titration cut point will be reported as the titer of the ADAs.

Tier IV Neutralizing Antibodies Assay: This is based on the principle that any sample containing NAbs would reduce or abolish the biological activity associated with a known concentration of drug product used in a cell-based NAb assay. This is based on the mechanism

of action of the drug (rituximab) and is used to characterize the neutralizing activity of the confirmed ADA-positive samples. Rituximab induces CDC. The ability of the ADA to neutralize the CDC activity of rituximab will be assessed in a cell-based assay. This assay is developed and will be validated prior to clinical sample analysis. This assay is a characterization of the confirmed ADAs.

The diagrammatic representation of the immunogenicity assessment of rituximab in the clinical study is shown in [Figure 6-1](#).

Figure 6-1: Flow Diagram for the Evaluation and Characterization of Anti-Drug Antibodies

Abbreviation: ADA, anti-drug antibody.

Comprehensive information regarding validity, specificity, and sensitivity of immunogenicity assays used in this study will be provided in a separate report.

6.3 Safety Assessments

The safety endpoints of this study are as follows:

- Incidence of TEAEs and SAEs.

- Incidence of anaphylactic reactions, hypersensitivity reactions, and IRRs.

Other safety endpoints will include the following:

- Clinical laboratory parameters
- Vital signs
- Twelve-lead ECG
- Physical examination

Definitions

Infusion-related Reactions

Infusion-related reactions are defined as a group of acute reactions to the allergen (or therapeutic protein for this study) that occur during or shortly after drug infusion and generally resolve completely within 24 hours of completion of infusion.

Signs/symptoms may include the following: allergic reaction (including drug fever), arthralgia (joint pain), bronchospasm, cough, dizziness, dyspnea (shortness of breath), fatigue (asthenia, lethargy, malaise), headache, hypertension, hypotension, myalgia (muscle pain), nausea, pruritis/itching, rash/desquamation, rigors/chills, sweating (diaphoresis), tachycardia, tumor pain (onset or exacerbation of tumor pain due to treatment), urticaria (hives, welts, wheals), and vomiting ([Doessegger L and Banholzer ML 2015](#)).

Hypersensitivity Reactions

Any AE, which occurs 24 hours of completion of infusion and with clinical or clinical laboratory (if performed) features suggesting an immunoallergic mechanism and without any other supported alternative explanation and not fulfilling the provided definition of anaphylactic reaction.

Hypersensitivity reactions to biologic agents are less common than standard IRRs. Although some clinical signs and symptoms are more unique to hypersensitivity reactions, many are similar. Hypersensitivity and standard IRRs can have gastrointestinal symptoms, dyspnea, flushing, pruritus, and back pain. Symptoms that are more suggestive of a hypersensitivity reaction would include urticaria, wheezing, frequent coughing, and anaphylactic symptoms ([Khan DA 2016](#)).

Anaphylaxis

Anaphylaxis is highly likely when any 1 of the following 3 criteria (criteria of the National Institute of Allergy and Infectious Disease/Food Allergy and Anaphylaxis Network), which will be applied for diagnosing anaphylaxis ([Sampson HA 2006](#)) are fulfilled based on the principal investigator's discretion or clinical evaluation:

1. Acute onset of an illness (minutes to several hours) with involvement of the skin, mucosal tissue, or both (e.g., generalized hives, pruritus or flushing, swollen lips-tongue-uvula) AND AT LEAST 1 OF THE FOLLOWING:
 - a. Respiratory compromise (e.g., dyspnea, wheeze-bronchospasm, stridor, reduced peak expiratory flow or hypoxemia).
 - b. Reduced BP or associated symptoms of end organ dysfunction (e.g., hypotonia [collapse], syncope, incontinence).
2. Two or more of the following that occur rapidly after exposure to a likely allergen for that subject (minutes to several hours):
 - a. Involvement of the skin mucosal tissue (e.g., generalized hives, itch-flush, swollen lips-tongue-uvula).
 - b. Respiratory compromise (e.g., dyspnea, wheeze-bronchospasm, stridor, reduced peak expiratory flow, hypoxemia).
 - c. Reduced BP or associated symptoms (e.g., hypotonia [collapse], syncope, incontinence).
 - d. Persistent gastrointestinal symptoms (e.g., crampy abdominal pain, vomiting).
3. Reduced BP after exposure to known allergen for that subject (minutes to several hours):
 - a. Infants and children: low systolic BP (age specific) or greater than 30% decrease in systolic BP (this study is going to be conducted in adult subject population, hence this criterion will not be applicable here).
 - b. Adults: systolic BP of less than 90 mmHg or greater than 30% decrease from that person's baseline.

Note: Above differentiating features of IRRs, hypersensitivity and anaphylaxis are recommendations based on the literature ([Doessegger L and Banholzer ML 2015](#), [Khan DA](#)

2016, Sampson HA 2006). The investigator should use his/her clinical judgment to document it as IRRs and/or hypersensitivity reactions and/or anaphylaxis.

The timing and frequency of safety assessments are described in [Section 6.1](#).

6.3.1 Adverse Events

6.3.1.1 Definitions

The definitions for AEs, SAEs, and TEAEs are given below. It is of the utmost importance that all site personnel involved in the study are familiar with the content of this section. The principal investigator is responsible for ensuring this.

6.3.1.1.1 Adverse Event/Reaction

An AE is defined as any untoward medical occurrence in a subject, or clinical investigation subject administered a pharmaceutical product, and which does not necessarily have a causal relationship with this treatment. An AE can therefore be any unfavorable and unintended sign, symptom, or disease temporally associated with the use of a study treatment, whether or not related to the study treatment.

Any relevant observations made at the screening visit (prior to signing the ICF) are to be recorded as a preexisting condition; an AE will only be recorded if there is a worsening of the preexisting condition during study conduct with regards to nature, severity, or frequency.

An ADR is an untoward and unintended response to a study treatment related to any dose administered. All AEs judged by either the reporting investigator or the sponsor as having a reasonable causal relationship to a medicinal product qualify as ADRs. The expression of “reasonable causal relationship” means to convey in general that there are facts or arguments meant to suggest a causal relationship.

A pre-treatment event is defined as any untoward medical occurrence in a clinical investigation subject who has signed informed consent to participate in a study but prior to administration of any study drug; it does not necessarily have to have a causal relationship with study participation.

Serious Adverse Event

An SAE is defined as an AE that results in 1 of the following outcomes:

- Results in death.

Death is not an AE/SAE itself, but an outcome. The cause of the death is an AE, which resulted in death.

- Is life-threatening.

Life-threatening means that the subject was at immediate risk of death at the time of the SAE, it does not refer to an SAE that hypothetically might have caused death if it were more severe.

- Requires in-subject hospitalization or prolongs existing hospitalization (This does not include prolonged hospitalization for study purposes).

Hospitalization is defined as at least 1 overnight formal admission into hospital, usually to perform additional tests, provide treatment that it is not possible to provide at home and/or to allow specific monitoring of the subject due to their unstable medical condition. Current hospitalization due to preplanned hospitalizations (known already prior to signing the ICF) will not be considered an SAE, unless any of the above criteria are fulfilled over the course of the hospitalization due to unplanned complications. Following the initial discharge from hospital, subsequent hospitalizations are to be considered an SAE. "Social" hospitalization, defined as administrative impossibility to discharge the subject is not necessarily an SAE. Complications that occur during hospitalization are AEs unless they would qualify as an SAE for any of the above criteria. If the complication delays the subject's release from hospital, then the AE becomes an SAE. Hospitalizations due to diagnostic procedures which are not performed due to an AE are not regarded as SAE.

- Results in persistent or significant disability/incapacity.

The term significant disability refers to any condition that impairs physical/psychological well-being to the extent that the subject is unable to function normally. Physical disability may include, but is not limited to, permanent disability of locomotion or motility, but also systemic permanent dysfunction as development of heart failure, liver insufficiency, or pulmonary fibrosis.

- Is a congenital anomaly/birth defect.

- Is an important medical event.

Important medical events that may not result in death, be life-threatening, or require hospitalization may be considered an SAE when, based upon appropriate medical judgment they may jeopardize the subject or the subject may require medical or surgical intervention to prevent 1 of the outcomes listed in this definition.

6.3.1.1.2 Treatment-Emergent Adverse Event

Treatment-emergent AEs are defined as any AE occurring or worsening on or after the first dose of study medication.

6.3.1.2 Recording of Adverse Events

Any relevant observations made at the screening visit (prior to signing the ICF) are to be recorded as a preexisting condition. For the purposes of this study, any detrimental change in the subject's condition, after signing the ICF and up to completion of the 26-week study period, should be considered as a TEAE/SAE.

The following variables will be recorded for each AE: verbatim/AE description and date for AE start and stop, severity, seriousness, causality rating, whether or not the AE caused the subject to discontinue, action taken with the study treatment, and the outcome. If the severity of the event changes, the event with the highest severity will be recorded.

Serious AEs and TEAEs will be recorded starting after signing of the ICF. All SAEs and AEs have to be recorded, whether or not considered causally related to the study treatment or to the study procedure(s).

All ongoing nonserious AEs should be followed up until resolution or stabilization or the EOS/ET visit, whichever occurs first, with the exception of any ongoing treatment-related nonserious AEs that should be followed until that AE is stabilized, resolved, or, in the investigator's opinion, the AE is unlikely to resolve due to the subject's underlying condition.

All ongoing SAEs should be followed up until resolution or stabilization/or until a pre-defined outcome is reached.

Note: Outcome information received on on-going SAE beyond the date of data base lock, will be captured in safety database and reported as follow-up report in the form of individual case safety report.

At any time after the additional follow-up visit, if an investigator learns of an SAE that can be reasonably related to study treatment, he/she should promptly notify the sponsor/designee.

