3.2.2 Contingency Measures Taken During the COVID-19 Pandemic

Based upon the above mentioned considerations, the following measures have been implemented in the study:

1. COVID-19 protective measures: Advice to the sites to implement general hygienic measures for both ongoing subjects and any new subject to educate on such protective and preventive measures.
2. Assurance of subject safety by investigator before enrolment (by COVID-19 related screening questionnaire).
3. Measures to be taken if investigator suspect COVID-19-related symptoms or if a subject is found positive to COVID-19.
4. In order to protect subject's safety and welfare, it is also recommended that site contacts subjects periodically (preferably on Day 7, 14; Weeks 6, 10, 14, 18, and 22) via telephone to inquire about his/her overall well-being, to seek information on alarm symptoms (fever, cough, breathlessness, COVID-19-related skin lesion, etc) of COVID-19 infection, information on subject's contact with any COVID-19-positive patient, and to guide the subject to take appropriate medical care.

If a study subject has an event suspected to be COVID-19 related, the investigator will have to decide on performing COVID-19 testing per local health authority or study site guidance.

Any new AE or change in the intensity of ongoing AE(s) with special focus on symptoms related to COVID-19, new medication(s) taken by the subject since his/her last visit, or any change in dose/frequency of medication(s), which is received, will be also documented in the source documents and eCRF.

5. Any event of COVID-19 is to be considered as an “Event of Special Interest” and all relevant detailed information will be collected, such as diagnosis, management and outcome. All events related to or linked to COVID-19 and meeting SAE criteria must be reported to **CI** Pharmacovigilance within 24 hours of the investigator’s knowledge of the event by facsimile or other appropriate method.

Moreover, due to current COVID-19 pandemic situation, remote source data verification may be performed per local regulations. All details of remote monitoring will be captured in the monitoring plan, if required.

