9.1. Adverse Events

An adverse event (AE) is defined as any untoward medical occurrence in a subject, or clinical investigation subject administered a pharmaceutical product, and which does not necessarily have a causal relationship with this treatment. An AE can therefore be any unfavorable and unintended sign, symptom, or disease temporally associated with the use of a study treatment, whether or not related to the study treatment.

A treatment-emergent AE (TEAE) is defined as an AE that meets any of the following conditions:

- Begins on or after the first dose of study drug.
- Begins before the first dose of study drug and worsens in severity on or after the first dose of study drug.

A SAE is defined as any untoward medical occurrence that at any dose results in death, is life-threatening, requires inpatient hospitalization or prolongation of existing hospitalization, results in persistent or significant disability/incapacity, is a congenital anomaly/birth defect or important medical event.

All adverse events will be classified by System Organ Class (SOC) and Preferred Term (PT) according to the Medical Dictionary for Regulatory Activities (MedDRA, Version 23.0 or higher or available latest version). The severity of the AE will be graded based on the Common Terminology Criteria for Adverse Events (CTCAE) v5.0 or available latest version. AEs that are missing a severity will be imputed as 'Severe' but will be presented in the listing with a missing severity.

All TEAEs and AE for rescue medication will be summarized and presented in a listing for the safety population.

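### Keeping only the highest severity of an AE means that worsening after the first dose, which the TEAE definition requires for a pre-dose AE, cannot be derived from the AE variables the protocol lists

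*Protocol*

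**What the plan says.** Protocol 6.3.1.2 (Recording of Adverse Events) lists what is recorded for each AE, beginning with "verbatim/AE description and date for AE start and stop, severity, seriousness, causality rating". The list goes on to discontinuation, action taken and outcome. There is one severity per event: "If the severity of the event changes, the event with the highest severity will be recorded".

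Protocol 6.3.1.1.2 defines a TEAE as "any AE occurring or worsening on or after the first dose of study medication". SAP 9.1 splits this into two conditions. The first is onset on or after the first dose. The second, for earlier onset, is "Begins before the first dose of study drug and worsens in severity on or after the first dose of study drug".

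Protocol 6.3.1.2 also contains a different rule: any detrimental change "after signing the ICF and up to completion of the 26-week study period, should be considered as a TEAE/SAE". That starts the clock at consent rather than at the first dose.

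Protocol 6.1.1 places screening within 14 days before the planned first day of treatment, and AEs are recorded from consent. TEAE and SAE incidence are primary safety endpoints (Protocol Table 2-1, SAP 3.2).

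**The concern.** The second SAP condition compares severity before and after the first dose. The recording rule keeps one value, the maximum, and the listed variables do not say when it was reached. The analysis definition therefore asks for information that the recording rule does not keep.

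The AEs affected begin between consent and first dose and are still ongoing at the first infusion. They include events that became worse after study treatment, some of which could belong in the grade 3 or higher and serious TEAE rows of the SAP 9.1.1 overview. Safety is assessed descriptively with 70 subjects planned per arm, so individual misclassifications are visible in the percentages.

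**Working it through.** No figure in the plan bears on this point, so there is none to reproduce. The check is whether the second SAP condition can be derived from the variables in Protocol 6.3.1.2.

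**Step 1: three histories, one record.** Take an AE that starts in screening, is ongoing at first dose, and reaches severe at some point.

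| History | Start date held | Severity held | TEAE under SAP 9.1 | If sorted by start date | If the consent wording of 6.3.1.2 is followed |
|---|---|---|---|---|---|
| Severe from onset | pre-dose | severe | no | no | yes |
| Mild, became severe before first dose | pre-dose | severe | no | no | yes |
| Mild, became severe after first dose | pre-dose | severe | yes | no | yes |

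The records are the same on onset and severity, but only the third history is a TEAE. Sorting by start date misses it. Following the consent wording counts all three. Neither shortcut reproduces the SAP definition.

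**Step 2: does another rule repair it?** SAP section 4 imputes incomplete AE stop dates. SAP 9.1 imputes a missing severity as severe. Protocol 7.4.2 promises conservative imputation of missing dates, severity and relationship. None applies, because no listed field is missing; the earlier grade was simply not kept. The SAP gives no default for unclear timing of worsening.

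**Step 3: what is not affected.** Under Protocol 6.3.1.1.1, worsening of a condition present before consent is itself recorded as an AE. AEs that start after first dose meet the first SAP condition. AEs that stopped before first dose are not TEAEs. An AE whose highest grade is mild cannot have risen in grade. What remains is AEs with a pre-dose start, ongoing at first dose and recorded as moderate or worse.

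**Step 4: scale.** One subject is 1/70 = 1.4 percentage points of an arm. This is the most one subject can move any row, and the any-TEAE row moves only if that subject has no other TEAE.

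The number of affected events is not in the documents. The following rests on assumptions:
- With a constant AE onset rate, the 14-day window holds 14/(14 + 84) = 14% of AEs recorded to Week 12, or 14/(14 + 182) = 7% of those recorded to Week 26.
- If 5% to 20% of these worsen after dosing, the affected share is 0.7% to 2.9% of AEs to Week 12, or 0.4% to 1.4% to Week 26.
- Counting subjects instead: if 5% to 20% of 140 have an AE ongoing at first dose and 10% to 30% of those worsen, the range is 140 × 0.05 × 0.10 = 0.7 to 140 × 0.20 × 0.30 = 8.4 subjects.

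**The case against.** The strongest reply is that the information may exist elsewhere and that no text sends these events out of the tables.

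- Protocol 3.2.2 says that "Any new AE or change in the intensity of ongoing AE(s) with special focus on symptoms related to COVID-19" "will be also documented in the source documents and eCRF". That is a real route to the data, and its focus on COVID-19 is not exclusive. But it belongs to the pandemic contingency measures, the same section lets the sponsor stop COVID-19-specific collection, and the SAP makes no use of it.
- Protocol 8.2 says the eCRF files keep their audit history. A grade entered before the worsening could therefore be traced. This helps recovery but does not supply an analysis variable.
- Protocol 6.3.5 has clinically significant examination changes after initial dosing recorded as AEs, and 6.3.7 covers worsening ECG findings. SAP 9.3 shows laboratory worsening in grade shift tables. Under Protocol 6.3.1.5, a nonserious AE that becomes serious must be reported within 24 hours. Infusion-related reactions are by definition of post-dose onset. Together these narrow the gap. None says how to record a general AE that began in screening and worsened after dosing.
- eCRF version 3.0, on which the SAP is based, is not among the documents. It may already split such records. If it does, it departs from the sentence in 6.3.1.2, which would still need changing.

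A reader might infer that the second TEAE condition can never be evaluated and that all such events move to Listing 16.2.7 (non-treatment-emergent AEs). The documents do not support that. No section prescribes classification by start date, 6.3.1.2 itself would count these events, and source documents or the audit history may recover the earlier grade.

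**Conclusion.** The gap is real and narrow. On the variables listed in Protocol 6.3.1.2, the worsening condition in SAP 9.1 and Protocol 6.3.1.1.2 cannot be derived, and the SAP offers neither a derivation nor a default. The protocol's two statements of when an AE is treatment-emergent also disagree. Depending on which convention the programmer adopts, worsened AEs may be omitted or AEs that did not worsen may be counted.

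The likely result is a small undercount in both arms. Recording is blinded and the same in both arms, so a bias toward one product is not expected. The problem is confined to AEs that start in the roughly 14-day screening window. Its size is not given, the ranges above rest on assumed rates, and the firm figure is 1.4 percentage points per subject per arm. All of this is conditional on the eCRF not already splitting records.

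The point should be corrected because a recording rule conflicts with the definition of a primary safety endpoint, even though no large loss of events has been shown.

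**What to change.** 1. **Recording.** Amend Protocol 6.3.1.2 and the eCRF guideline. When an AE that began before the first infusion worsens on or after it, close the record and open a new AE with the date of worsening and the new grade. Keep the highest-severity rule for changes that lie wholly after first dose.
2. **Records already entered.** Before database lock, query AEs with a pre-dose start that were ongoing at first dose, using source documents and the eCRF audit history. Under the SAP's severity criterion, only those graded above mild need the question.
3. **SAP 9.1.** State how worsening is derived. Add a default: a pre-dose AE ongoing at first dose with unclear timing of worsening counts as a TEAE.
4. **Wording.** Reconcile the statement in Protocol 6.3.1.2 that detrimental changes after consent are TEAEs/SAEs with Protocol 6.3.1.1.2 and SAP 9.1.

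The cost is a short protocol and SAP edit, a guideline change and a few queries. The downside is a slightly higher TEAE count, because the default will include some AEs that did not worsen after dosing.
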